12.1 Sample size

The median disease-free survival was 60 months in 60% of the patients who received the standard medical treatment, and in 85% of those who received the UC-MSC therapy. Assuming a recruitment period of 40 months and a total follow-up period of over 75 months, with 100 patients in each group, the study would need to have power greater than 80% to detect a significant relative risk reduction, at a two-sided α level of 0.05 (PASS 11.0). Based on the dropout or withdrawal rate, we determined a sample size of 125 patients per group.

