12.2 Definition and selection of analysis sets

This study used three data sets: A safety set, a full analysis set, and a per-protocol set.

Safety set (SS): SS refers to the set of all subjects who received at least one UC-MSC infusion and had a post-treatment safety record. The SS will be used for safety analysis and the subjects will be analyzed according to the actual treatment received.

Full analysis set (FAS): FAS refers to the set of all subjects who randomly received at least

one UC-MSC infusion. When the main efficacy indicators are missing, the missing data is not filled in, and will be assigned to the unresponsive set. FAS is the primary analysis set and will be used to report the distribution, demographic data, baseline characteristics, compliance, and efficacy evaluation for all subjects. The subjects will be analyzed in a randomized treatment group.

Per-protocol set (PPS): PPS refers to the set that the subjects coincide with the major inclusion criteria, do not coincide with the major exclusion criteria, complete the treatment regimen, do not take banned medication during the trial, and have no other major program violations. PPS will be used to evaluate primary efficacy.

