12.3.4 Efficacy analysis

The efficacy analysis will be based on the FAS set. PPS analysis will serve as an ancillary analysis for FAS. If the PPS results are inconsistent with the FAS results, it will be necessary to analyze and discuss the possible causes.

(1) Primary efficacy

All eligible participants who receive the assigned treatment and are followed up will be included in the analysis. We will count the number of endpoint events (death or HCC events) that occurred during the follow-up period and will compare the event-free time between the two groups using Kaplan–Meier analysis. The post-treatment follow-up will be continued until the date of an endpoint event, death, or the end of the study, whichever occurs first. Cox proportional-hazards models will be developed to estimate the hazard ratio (HR) and 95% confidence interval (CI) for between-group comparisons, with or without adjustments for stratification baseline MELD scores. Additionally, we will perform landmark analyses to assess the endpoint events accordingly, with the hazard ratio calculated separately for events that occurred before or after the landmark points.

(2) Secondary efficacy indicators

Liver function: The serum levels of ALB, PTA, CHE, and TBIL will be monitored within 48 weeks after the first UC-MSC infusion or routine medical treatment. A paired t-test will be applied to analyze the levels of ALB, PTA, CHE, and TBIL of the participants in each group post-treatment compared with those at baseline. The levels of ALB, PTA, CHE, and TBIL of the participants will also be compared between the treatment group and the control group at each specific evaluation timepoint. Student's t test or a non-parametric test will be applied when relevant.

Complications: MedDRA will be used to code and classify complications. For all cases, the

episode and severity of the complication will be listed by groups. The incidence by each study group and severity, respectively, will be calculated. The incidence between groups will be compared using the Chi-squared test or Fisher's exact test. Multiple Chi-squared comparisons will be performed on the basis of a Bonferoni-adjusted α value when relevant.

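### The 48-week secondary tests have no rule for death or withdrawal: the liver-function comparison is conditional on being alive and sampled, and crude complication incidence ignores length of observation

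*Protocol*

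**What the plan says.** Protocol section 7.2 sets the liver-function evaluations at weeks 12, 24 and 48. Section 12.3.4 (2) prescribes paired t-tests against baseline within each arm, and between arms the levels are "compared between the treatment group and the control group at each specific evaluation timepoint" by Student's t or a non-parametric test. For complications, "The incidence between groups will be compared using the Chi-squared test or Fisher's exact test".

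The one missing-data rule is in section 12.2: "When the main efficacy indicators are missing, the missing data is not filled in, and will be assigned to the unresponsive set". It is limited to the main efficacy indicators.

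The protocol records complications at each visit from week 2 to week 48 (sections 6.4 to 6.9) and lists them for all cases (12.3.4). It records the time of death (7.1) and asks for data and an examination at withdrawal (4.3, 6.14, 10.2). It does not give the denominator for complication incidence, or say how a patient with short follow-up is classified.

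Section 12.1 assumes disease-free survival "in 60% of the patients who received the standard medical treatment, and in 85% of those who received the UC-MSC therapy", and then: "Based on the dropout or withdrawal rate, we determined a sample size of 125 patients per group".

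**The concern.** A visit-wise test drops everyone who has died or left by that visit. The population has decompensated cirrhosis, survival is a primary endpoint, and the plan expects control patients to fail about three times as fast. The patients remaining at week 48 would then be selected differently in the two arms. If those who die tend to have the worse liver function, the arm with more deaths keeps a healthier-looking remainder. The within-arm paired tests likewise describe change among those who remain.

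The section 12.2 rule does not help. It does not name these endpoints, and a continuous level has no unresponsive category. An examination at withdrawal does not supply a week-48 value, and nothing can supply one after death.

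For complications, a patient who withdraws at week 4 without an event is either counted as complication-free for 48 weeks or left out. The text permits both. The first under-counts; the second restricts the comparison to those who stayed. At stake is the reading of both secondary efficacy results.

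**Working it through.** **Inputs.** From section 12.1: 60% (control) and 85% (UC-MSC), read as event-free at 60 months because the sentence is garbled; 100 per arm before and 125 after allowance for dropout. Week 48 is 48 × 7 / 30.4375 = 11.04 months. The protocol gives no laboratory SD, 48-week mortality or complication rate, so laboratory results are in SD units and the complication risks are assumed.

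**The plan's own figure.** The plan states power above 80% with 100 per arm "at a two-sided α level of 0.05". Two-proportion normal approximation:
- SE under the null = √(2 × 0.725 × 0.275 / 100) = 0.0631
- SE under the alternative = √((0.60 × 0.40 + 0.85 × 0.15) / 100) = 0.0606
- power = Φ((0.25 − 1.96 × 0.0631) / 0.0606) = Φ(2.08) = 98.1%

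This satisfies the stated inequality. Separately, 100 / 0.80 = 125, so the implied dropout is 20%.

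**Early events.** With constant hazards:
- control: −ln(0.60) / 60 = 0.00851 per month
- UC-MSC: −ln(0.85) / 60 = 0.00271 per month, a ratio of 3.1
- by week 48: 1 − exp(−11.04 × 0.00851) = 9.0% and 1 − exp(−11.04 × 0.00271) = 2.9%, or about 11 and 4 of 125

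On this reading these are upper figures for death, because they include HCC and a patient with HCC can still be sampled.

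**Liver function, no true effect.** Let the sickest fraction q die, and let frailty correlate ρ (assumed) with the week-48 level. The survivors' mean shifts by ρ × φ(z_q) / (1 − q) SD towards health:
- control: φ(−1.343) / 0.910 = 0.178, times ρ
- UC-MSC: φ(−1.889) / 0.971 = 0.069, times ρ
- SE with 113.8 and 121.3 survivors = √(1/113.8 + 1/121.3) = 0.1305 SD

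| ρ | Control shift (SD) | UC-MSC shift (SD) | Bias against UC-MSC (SD) | Bias / SE |
|---|---|---|---|---|
| 0.3 | 0.053 | 0.021 | 0.033 | 0.25 |
| 0.5 | 0.089 | 0.035 | 0.054 | 0.42 |
| 0.7 | 0.125 | 0.048 | 0.076 | 0.58 |

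At ρ = 0 the bias is zero. A true 0.4 SD benefit would appear as 0.346 SD (ρ = 0.5) or 0.324 SD (ρ = 0.7). Power would fall from 88% with 125 per arm to 75% or 70%.

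**Complications, death only.** Use cumulative hazards over 48 weeks: λ for complications, μ for death (0.0940 control, 0.0299 UC-MSC). Observed incidence = λ / (λ + μ) × (1 − exp(−(λ + μ))). With the same underlying risk in both arms:
- 20%: 19.1% against 19.7%
- 30%: 28.7% against 29.6%
- 40%: 38.3% against 39.5%
- 50%: 48.0% against 49.3%

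The gap is 0.6 to 1.4 points. The same formula is the competing-risk cumulative incidence, so that method returns the same numbers. Complication-or-death at 30% risk is 1 − exp(−(0.3567 + 0.0940)) = 36.3% against 1 − exp(−(0.3567 + 0.0299)) = 32.1%, which reverses the direction.

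**Complications, adding withdrawal (40% risk).** Add a withdrawal hazard to μ. The dropout splits are assumed:
- 28% control and 12% UC-MSC, all within 48 weeks: 33.2% against 37.3%
- 12% control and 28% UC-MSC, all within 48 weeks: 36.2% against 34.1%
- 28% control and 12% UC-MSC, spread evenly over 75 months: 37.5% against 39.1%

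An overall 20% spread over 75 months is 1 − 0.80^(11.04/75) = 3.2% by week 48.

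**The case against.** A reader might infer that patients who die or leave before week 48 cannot be scored at all. The protocol does not support that: liver values count at each visit reached, and a complication recorded before exit is kept.

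A reader might also infer that such patients are counted as complication-free. No denominator is stated, so this is one of two readings, and it concerns only those without an earlier complication.

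A third tempting inference is that complication incidence is shown to favour the arm with more early deaths by several points. The death component is about 1 point, and a competing-risk estimate would show it too. It is the correct incidence of complications when death intervenes, so the issue is interpretation. A 4-point gap needs all dropout placed in the first 48 weeks with a split that has no source in the document; reversing the split changes the sign.

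It can also be said that death is already a primary endpoint with its own analysis, that ranking death worst changes what the secondary endpoint measures, and that an analysis plan not shown may settle missing secondary data. The first two points stand, so the rank analysis should be supplementary. The third stands in part: the protocol already fixes these tests, and the rule it gives does not fit them.

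**Conclusion.** The point holds in limited form. As written, the liver-function comparison is conditional on being alive and measured, crude complication incidence takes no account of observation time, and the section 12.2 rule covers neither.

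The laboratory bias is modest: 0.03 to 0.08 SD, or 0.25 to 0.58 SE. It rests on constant hazards, the 60-month reading of section 12.1, an event rate that includes HCC, and assumed correlations of 0.3 to 0.7. It would run against UC-MSC if UC-MSC lowers mortality and in its favour if it raises mortality. Unequal dropout could offset or add to it.

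For complications, the real under-counting comes from withdrawals. Neither its size nor its direction can be fixed from the protocol. The matter concerns secondary endpoints, leaves the primary survival analysis untouched, and is worth correcting because the correction is cheap.

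**What to change.** 1. **Liver function.** Keep the visit-wise comparison and state that it is conditional on being alive and measured. Add a supplementary week-48 Wilcoxon comparison with deaths before week 48 ranked worst. Handle living withdrawals by a stated rule, for example multiple imputation from earlier visits. The result mixes death with liver function, so it is read beside the means.
2. **Complications.** Analyse time to first complication over 48 weeks, counted from week 0 in both arms, with withdrawal censored and death as a competing event (cumulative incidence, Gray's test). Add complication-or-death as a sensitivity analysis, because the competing-risk estimate alone does not count death against an arm. Censoring assumes that withdrawal is unrelated to the coming risk of a complication, and the text should say so.
3. **Reporting.** Show deaths and withdrawals before week 48 by arm beside both results.

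The cost is wording and a little programming, with no new visits. Time of death and complications at every visit to week 48 are already recorded; the case report form should be checked for onset dates of complications and dates of withdrawal.

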12.4 Statistical software and general requirements

(1) Analysis will be performed using SAS 9.2 or newer;

(2) The estimated overall survival rate and HCC-free survival rate, as well as bilateral 95% confidence intervals, will be calculated;

(3) Unless there is another declaration, the hypothesis testing will be two-sided with an α value of 0.05.

13 Clinical trial management

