3.2 Endpoints

3.2.1 Primary endpoints

(1) Survival rate during 75 months posttreatment follow up.

(2) Hepatocellular carcinoma (HCC)-free survival rate during 75 months of posttreatment follow up.

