3.3 Randomization

Patients will be randomly allocated to the conventional treatment (control) or UC-MSC treatment (UC-MSC infusion) groups at a 1:1 ratio according to a computer-generated randomization list. The randomization list will be generated by third party statistical staff. The randomization code will be assigned to a participant at his or her first visit. The participants will be assigned to the treatment groups corresponding to the randomization code. This is an open-label study; both participants and the study team will be aware of the treatment allocation.

4 Participants

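### Two primary endpoints are each tested at two-sided 0.05 with no rule for combining them, so the false-positive rate is about 6.5% to 9% if either one can carry the claim

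*Protocol*

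**What the plan says.** Section 3.2.1 lists two primary endpoints without ranking them: "Survival rate during 75 months posttreatment follow up" and "Hepatocellular carcinoma (HCC)-free survival rate during 75 months of posttreatment follow up". The Synopsis lists the same two and calls the first overall survival.

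Section 12.4 gives one general rule on significance: "Unless there is another declaration, the hypothesis testing will be two-sided with an α value of 0.05". The only other declaration is in section 12.3.4, where a Bonferroni-adjusted level applies to multiple chi-squared comparisons of complications.

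On the primary analysis, section 12.3.4 says "We will count the number of endpoint events (death or HCC events) that occurred during the follow-up period" and that event-free time is compared by Kaplan–Meier analysis. Cox models then estimate the hazard ratio, "with or without adjustments for stratification baseline MELD scores". Landmark analyses are added, "with the hazard ratio calculated separately for events that occurred before or after the landmark points", with no landmark times given. The section does not say which of these decides.

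Section 3.3 describes 1:1 allocation "according to a computer-generated randomization list" and mentions no strata. Section 12.1 powers a single comparison of disease-free survival at two-sided 0.05.

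**The concern.** When two endpoints are both primary and each is tested at 0.05, a trial of an ineffective treatment has two chances to look positive. Unless the plan says that both must be significant, or sets an order or a split of alpha, a significant result on one alone can be reported as a primary success. The type I error of that claim is then above 5% for any correlation below 1. The authors controlled multiplicity for complications but left the two primaries at the default level.

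A second, smaller freedom comes from the MELD wording. With neither version of the Cox model named as deciding, the choice could be made after both results are known. The trial is open label, so fixing these choices in advance matters more than usual.

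**Working it through.** **Inputs from the protocol.** Two primary endpoints (3.2.1); two-sided 0.05 for each (12.4); 60% versus 85%, 40 months of recruitment, 75 months in total, 100 per group before allowance for dropout, 125 per group enrolled (12.1). Section 12.1 calls the 60% and 85% figures medians. I read them as disease-free proportions at 60 months, because as worded they cannot be medians.

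**Assumptions.** The protocol gives no correlation between the endpoints, no HCC rate and no mortality after HCC. These are assumed, and ranges are shown.

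**Step 1: the plan's own power figure (above 80% at 0.05, 100 per group).**
- Two proportions, pooled variance under the null: 98.1%.
- Exponential survival: HR = ln(0.85)/ln(0.60) = 0.318. Monthly hazards are 0.00851 and 0.00271. Uniform accrual over 40 months and 75 months in total give event probabilities of 0.371 and 0.138, so 100 × (0.371 + 0.138) = 50.9 events.
- Schoenfeld: Φ(½ × √50.9 × 1.145 − 1.960) = Φ(4.085 − 1.960) = 98.3%.
- Freedman: Φ(√50.9 × (1 − 0.318)/(1 + 0.318) − 1.960) = Φ(3.690 − 1.960) = 95.8%.

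The stated power is reproduced, for one endpoint only.

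**Step 2: chance of at least one false positive with two tests at 0.05.** If independent, 1 − 0.95² = 9.75%. For correlated test statistics it is 1 − P(|Z₁| < 1.960 and |Z₂| < 1.960) under a bivariate normal:

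| Correlation | Either endpoint, 0.05 each | Either endpoint, 0.025 each |
|---|---|---|
| 0 | 9.75% | 4.94% |
| 0.59 | 8.8% | 4.5% |
| 0.70 | 8.4% | 4.3% |
| 0.90 | 7.0% | 3.6% |
| 0.95 | 6.5% | 3.3% |
| 0.99 | 5.7% | 2.9% |

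**Step 3: what correlation is plausible.** Log-rank tests were simulated under no treatment effect: 125 per arm, 75 months each, 10,000 runs per setting, 60-month survival of 60% to 85%, HCC incidence of 2% to 8% per year, mortality tripled after HCC, and HCC-free survival counting death or HCC. The correlation was 0.59 to 0.94. Each test alone rejected in about 5% of runs, at least one in 6.7% to 8.9%, and both in 1.3% to 3.4%. A separate simulation with 100 per arm in the 40/75-month design gave correlations of 0.76 to 0.95 and 6.5% to 8.0% for at least one.

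**Step 4: choosing between adjusted and unadjusted models.** With an assumed correlation of 0.90 to 0.98 between the two models, taking the better one gives 6.0% to 7.1% for a single endpoint. With both endpoints (between-endpoint correlation 0.5 to 0.9) it gives 8.3% to 12.6%. This applies only if either model may decide.

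**Step 5: power at 0.025 (critical value 2.241), same inputs as Step 1.** Two proportions 96.3%; Schoenfeld Φ(4.085 − 2.241) = 96.7%; Freedman Φ(3.690 − 2.241) = 92.6%.

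**The case against.** The strongest reply is that the excess depends on a success rule that the protocol never states. If both endpoints had to be significant, the simulated error would be 1.3% to 3.4%, below 5%. This stands as a condition on the figures. It is not a defence of the text, because no section contains such a rule. A statistical analysis plan, which is not at hand, could carry another declaration, but the protocol's own default applies to both endpoints as written.

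Section 12.3.4 can also fairly be read as one Kaplan–Meier comparison per endpoint, with adjusted and unadjusted hazard ratios reported as estimates. On that reading the MELD choice adds nothing. It therefore stays a secondary part of the point.

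A reader might infer more than the text supports in three places:
- **Landmark analyses.** The missing landmark times might suggest a much larger inflation. These analyses are introduced as additional, nothing ties them to a primary claim, and their times may be left to an analysis plan.
- **Stratification.** Section 12.3.4 might seem to contradict section 3.3. But 3.3 is silent on strata; it does not say that the list is unstratified. The word may also mean MELD categories used as a covariate. This is a wording query.
- **Power gain from MELD adjustment.** Any such figure needs a MELD effect, which the protocol does not give. At the effect it does imply (HR about 0.32), power is already about 96% to 98%, so little could be gained.

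**Conclusion.** The point holds in this form: two primary endpoints, each at two-sided 0.05, with no split, order or joint-success rule. If either can carry the claim, the family-wise error is about 6.5% to 9% (assumed correlation 0.95 to 0.59), with 9.75% under independence. The assumed rates move the size of the excess; its existence needs only a correlation below 1. An open choice between the MELD-adjusted and unadjusted models would add somewhat more.

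The definition of HCC-free survival also affects the size. Section 12.3.4 counts death or HCC, while section 9 records time to HCC alone. The simulated correlations use the first definition.

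A reader might also take the power in Step 5 as covering both primaries. It does not: section 12.1 gives an effect for disease-free survival only, so power for overall survival is unknown at 0.05 and at 0.025.

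**What to change.** Add to section 12.3.4 a statement such as: *The two primary endpoints are tested with Holm's procedure at a family-wise two-sided level of 0.05; the smaller p-value is compared with 0.025 and, if significant, the other with 0.05.* A fixed testing order, or a requirement that both be significant at 0.05, would serve equally well. Refer to the chosen rule from section 12.4.

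In the same section, name one deciding analysis per endpoint, make the other MELD version a sensitivity analysis, and state that the landmark hazard ratios are descriptive. Reconcile the word stratification with section 3.3: either describe the strata there or reword 12.3.4.

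The cost is wording. With Holm, the stricter step lowers power for the stated disease-free effect from about 96–98% to about 93–97% with 100 per group, and 60 per group would already give 80% at 0.025 (two proportions). No extra patients are needed for that effect. A fixed order, or requiring both, keeps 0.05 for each test, though requiring both lowers the chance of overall success by an amount that cannot be computed without an effect for overall survival.

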13.1 Compliance with GCP requirements

This clinical trial will be carried out in accordance with the requirements of GCP in China.

13.2 Protecting the privacy of the subject

When filling out and managing the CRF, protecting the subject's privacy should be considered, for example, using a serial number to represent the subject. Moreover, the abbreviation of the subject's name can be used as a proxy for the name.

13.3 Informed consent form.

Before starting the study, the subject informed consent must be explained to each subject participating in the study by the investigator in a way that the subject can understand, and the subject's voluntary informed consent must be obtained in written form. The date of receipt of written informed consent should be entered into the CRF. The following information will be explained to the subjects:

(1) The purpose of the trial;

(2) The research process;

(3) Benefits and risks;

(4) Other alternative treatments;

(5) Subject rights: Subjects will not be adversely affected if they refuse to participate in this study;

(6) At any time, the subject may withdraw from the study without adverse effects;

(7) A confidentiality agreement;

(8) What the subject must follow;

(9) Anything that may protect the interests of the subject.

